10.6. Safety Endpoint

Safety: The occurrence of all adverse events, by subject. The totality of the safety data will be summarized and presented. Safety events will be reported for all in-office subjects in which the lidocaine solution was introduced into the ear, or introduction of TDS in ear for OR lead-in subjects) (see **Section 13.2.3**), [REDACTED]

[REDACTED]
[REDACTED]
[REDACTED]

Safety data will be presented separately as follows:

- Lead-In OR Cohort
- Lead-In Office Cohort*
- Pivotal Cohort*

[REDACTED]
[REDACTED]

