11.4.4. Otoscopy

An otoscopic exam will be conducted for both ears in all subjects at screening, for all ears intended for treatment at procedure and for all treated at the follow-up visits. The otoscopic examination will be used to visually examine the condition of the external ear canal and TM. Routine ear cleaning may be conducted only to the extent necessary to ensure the tympanic membrane and ear canal are free from matter that may interfere with iontophoretic delivery and to ensure visualization of the tympanic membrane. Ear cleaning at the screening visit is required. Patients who are uncooperative during ear exam and ear cleaning at screening are not eligible study candidates.

The exam will be used to confirm eligibility, to assess the ear canal and TM for changes or adverse effects, and to inspect for residual drug prior to tube placement. In addition, appearance and patency of the tympanostomy tube and appearance of the myringotomy wound will be evaluated post-procedure and at the post-procedure follow-up visits. Presence or absence of middle ear effusion will be assessed.

The screening otoscopic exam may be conducted up to 28 days prior to procedure. Otoscopic examination is considered standard of care for this patient population and may be obtained prior to study informed consent as a screening assessment within 28 days prior to procedure.

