11.7.2. Earset Sizing

The IPS Earset is available in 6 sizes. The ear sizing procedure will be performed according to the Instructions for Use (IFU) provided with the IPS. If the subject's ear is not compatible with the ear plug and fit cannot be established to ensure the earplug can properly seal in the ear canal, the subject will be considered a screening failure.

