11.7.4. Earset Placement and Drug Instillation

Baseline tolerability will be assessed before placement of the Earset. The Earset ear plug of the size determined in the ear sizing procedure is then placed into the ear canal. Once the ear plug is positioned, the protective liner is removed, exposing the PSA to the ear canal.

Circumferential pressure is applied through the ear plug against the surface of the ear canal, ensuring adhesion of the PSA. The Earset's integrated fill system is used to instill the selected drug into the ear canal. This process is repeated for the second ear.

The Electrode Cable is snapped to the Return Electrode Patch. The Electrode Cable connects the Earsets and the Control Unit. The Return Electrode Patch is then attached to the patient at a clean, dry site (such as the shoulder near the base of the neck) that is clear of lesions, bony protuberances and excessive hair. Prior to placing the return electrode on the patient, the investigator will assess the location for pre-existing erythema using the five point Draize erythema score where 0 indicates no erythema, 1 = very slight erythema (barely perceptible), 2 = well-defined erythema, 3= moderate to severe erythema , 4= severe erythema to slight eschar formation.⁶⁵ Category 4 also includes visible blister or burn. The location will be assessed again following iontophoresis.

In the event that drug has been introduced into the ear and iontophoresis was not initiated, the subject will return for a follow-up visit 2 to 5 days post procedure to complete all assessments required at the 3-week visit since drug will have been introduced into the ear. This subject is included in the Safety Analysis Set, but is not considered a discontinued procedure since iontophoresis was not initiated and is therefore not included in the Full Analysis Set. The subject may then be exited from the study after the follow-up visit if no unresolved device, procedure or drug-related adverse events are present. If there are unresolved adverse events, the subject must also return for the scheduled 3-week follow-up visit. However, if the subject plans to undergo tube placement in the OR, the subject's subsequent procedure success will be documented as described in **Sections 10.8.5 and 11.7.10**. This subsequent procedure must take place within 2 months of the study procedure. No additional follow-up is required following this non-study tube placement procedure.

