11.11. Summary – Study Flow and Study Evaluations

The flow of subject participation, visits and evaluations is depicted as a schematic in **Figure 11**.

*Otoscopic examination, tympanometry and audiometry are considered standard of care for this patient population. Data obtained from these assessments within 4 weeks prior to study informed consent may be included as screening assessments.

† If tube(s) have been confirmed to have extruded, no additional follow-up visits are required and the subject may exit prior to the 24 month visit.

Figure 11. Schematic of Study Design Flow

The schedule of evaluations for each study visit is presented in **Table 4**.

Table 4. Table of Evaluations

Evaluation	Screening	Procedure	3 Weeks (-/+ 7 days)	6, 12, 18, 24 months [†] (-/+ 28 days)
Informed Consent	✓			
Medical History	✓			
Cranial Nerve Physical Exam*	✓	✓	✓	
Concomitant Medications	✓	✓	✓	✓
Inclusion/ Exclusion Criteria	✓	✓		
Otoscopy	✓ (**within 28 days prior to Procedure)	✓	✓	✓
Tympanometry	✓ (**within 28 days prior to Procedure)		✓	✓
Audiometry	✓ (**within 28 days prior to Procedure)		✓	
Procedure		✓		
Anesthesia Effectiveness*		✓		
Tube Placement Tolerability*		✓		
Suction Tolerability*		✓		
Post-Procedure Tolerability		✓		
Adverse Events		✓	✓	✓
Study Exit				✓

*Anesthesia effectiveness, cranial nerve physical exam and tolerability assessments for in-office subjects only.

** Otoscopic examination, tympanometry and audiometry are considered standard of care for this patient population. Data obtained from these assessments within 28 days prior to procedure may be included as screening assessments.

† If tube(s) have been confirmed to have extruded, no additional follow-up visits are required and the subject may exit prior to the 24 month visit.

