12.0 ASSESSMENT OF SAFETY

12.1. Adverse Events

All reported or observed adverse events that occur during or after the procedure will be recorded. The study Investigator will determine whether an adverse event has occurred, whether life-threatening, serious or non-serious. Pre-existing conditions should not be reported as adverse events unless there has been a worsening in the severity or frequency, which cannot be attributed to natural history or progression of the disease. This definition does not depend on the causal relationship with the device, drug or protocol requirements.

Any change of clinical significance, including vertigo, nausea and vomiting, derived from the protocol evaluations including observations and patient-reported findings will be included as adverse events. Adverse events will also include operative and recovery observation for lead-in procedures conducted in the OR with general anesthesia including, but not limited to, clinically-meaningful vital sign changes, emergence delirium, post-operative nausea, vomiting, disorientation, and complications related to intubation or induction.

All Adverse Events (AEs) will be recorded on dedicated AE case report forms. The event, date of onset, severity, seriousness, duration, treatment, outcome, date or resolution and relationship to device, procedure or drug will be recorded on the AE case report form (CRF). AEs will be categorized by seriousness, relatedness to procedure, investigational drug, or device whether anticipated or unanticipated. All adverse events will be coded using standard terms.

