13.2.3. Safety Analysis Set

The Safety Analysis Set will include all pivotal cohort subjects in whom the lidocaine solution is introduced into the ear canal.

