6.3 Safety Analysis Set

The Safety Analysis Set will include all pivotal cohort subjects in which the lidocaine solution is introduced into the ear canal.

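### In-office children enter the safety set only when lidocaine is instilled, so non-serious harms from earlier sizer or Earset contact can fall outside its rates; adverse event recording also starts after the ear cleaning required at screening

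*Protocol*

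**What the plan says.** Two rules decide whether a harm reaches the safety tables: who is counted, and from when.

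**Who is counted.** Protocol 10.6 reports safety events for all "in-office subjects in which the lidocaine solution was introduced into the ear, or introduction of TDS in ear for OR lead-in subjects". Protocol 13.2.3 states: "The Safety Analysis Set will include all pivotal cohort subjects in whom the lidocaine solution is introduced into the ear canal". SAP 6.3 repeats the rule, taking "all pivotal cohort subjects in which the lidocaine solution is introduced into the ear canal". Protocol 13.6 ties both the recording and the analysis of adverse events to this set.

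**From when.** Protocol 12.1 states: "All reported or observed adverse events that occur during or after the procedure will be recorded". In Table 4 (Protocol 11.11) the row "Adverse Events" is ticked at the procedure, at 3 weeks and at the later visits, but not at screening.

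**What happens to the ear before lidocaine.** Protocol 11.4.4 states: "Ear cleaning at the screening visit is required". At the procedure the ear is sized (11.7.2); if the plug cannot be made to fit and seal, "the subject will be considered a screening failure". The Earset is then placed (11.7.4): "Once the ear plug is positioned, the protective liner is removed, exposing the PSA to the ear canal". The adhesive is pressed around the canal wall, and only after that is the drug instilled.

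**The concern.** The study evaluates a drug and device system and is meant to support a marketing application (Protocol 10.1). An OR lead-in child enters safety reporting when the Tube Delivery System enters the ear, which is contact with a device. An in-office child enters on contact with the drug, although parts of the Iontophoresis System have already touched the canal by then.

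Children who stop between those two points may be the ones who tolerate the device least. If so, leaving them out makes the Iontophoresis System look better tolerated than it is. The start of recording raises a second, separate problem: cleaning is a required study step, exclusion 7 itself recognises that cleaning can abrade or irritate the canal, and no adverse event form is scheduled at that visit.

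**Working it through.** The plan gives no figure for children who stop before instillation or for their injury rate, so there is nothing to reproduce. The check sets the rules against the order of ear-contact steps.

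| Step | Reached by adverse event recording? | In the Safety Analysis Set if the child goes no further? |
|---|---|---|
| Cleaning required at screening (11.4.4) | No: before the procedure, no tick in Table 4 | No |
| Earset sizing (11.7.2) | It can be: the step sits under 11.7 Procedure, and the definition in 12.3 covers device use | No |
| Adhesive Earset placement (11.7.4) | It can be, for the same reasons | No |
| Lidocaine instilled, no current (11.7.4) | Yes | Yes, with a visit at 2 to 5 days |
| Current started (11.7.5) | Yes | Yes, and in the Full Analysis Set (13.2.1) |

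1. **Sizing and placement.** These events can be recorded. The gap is in the counting, because the set requires lidocaine and 13.6 uses the set. One ambiguity remains: the start of the procedure is not defined. Section 11.7.5 defines only the start of iontophoresis.

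2. **The neighbouring case is covered.** Section 11.7.4 deals expressly with drug instilled but no current, and places that child in the Safety Analysis Set. No visible text does the same for Earset contact without drug.

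3. **Screening cleaning.** This falls before recording starts. If the child goes on to treatment, the injury can also be absorbed into baseline: 12.1 does not count a pre-existing condition unless it worsens, and SAP 22.1 takes the last observation before the procedure as baseline.

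4. **Direction of the error.** Let *n* children be in the set with *x* having an event, and let *m* have device contact without drug, *y* of them with an event. The set reports *x*/*n*; the rate over all device contact is (*x* + *y*)/(*n* + *m*). The count is too low whenever *y* > 0. The rate is too low exactly when *y*/*m* > *x*/*n*, that is, when events are commoner in the children who stopped. That is plausible but not shown. Neither *m* nor *y* is in the documents.

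5. **The base.** The 222 pivotal children are those with evaluable data, and the footnote to Protocol 10.3 takes screening failures and withdrawals before the procedure out of that count. The *m* children are therefore additional to the 222, not a share of them.

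**The case against.** There are several fair points in favour of the plan as written.

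- **Redaction.** The sentence in 10.6 runs into redacted text, the two in-office cohorts there carry asterisks with no visible note, and SAP 14.1 is redacted just before its matching list of cohorts. A reader might infer that these children appear in no safety table at all. That cannot be asserted. The definitions in 13.2.3 and SAP 6.3 are unredacted and contain no exception, so the statement about the set stands.
- **Follow-up.** A reader might infer that such a child has no follow-up visit. Section 11.9 requires all subjects to return at 3 weeks, and 15.1 encourages those who do not complete the procedure to stay for evaluations. Neither clearly reaches a screening failure, but the blanket statement is not supported.
- **Self-concealing exclusion.** A cleaning injury could trigger exclusion 6 (damaged canal skin), and a reader might infer that the harm then hides itself. SAP 7.0 tabulates screening failures with reasons, so the exclusion would be visible, though not as an adverse event.
- **Other capture.** Serious events are notified at any time in the study (12.2), and enrolment begins at consent (10.4.1). SAP 14.1 and 21.0 promise listings. SAP 14.5 tabulates abnormal canal findings at screening for children in the set. FLACC scoring (11.4.9) has an Earset phase. These limit the gap to non-serious events and to counts and rates.
- **The OR comparison.** OR lead-ins also have screening cleaning and enter only when the Tube Delivery System is in the ear, so their rule ignores earlier contact too. Where to anchor a safety set is partly a matter of choice. The comparison shows only that the protocol already uses device contact as an entry point.
- **Standard of care.** Screening otoscopy may precede consent (11.4.4), so some cleaning is not clearly a study act.

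**Conclusion.** The point holds in a limited form. An in-office child with sizer or adhesive Earset contact who stops before instillation is outside the Safety Analysis Set. A non-serious harm from that contact would be left out of the set's counts and rates, though it may be recorded and listed. Separately, a non-serious injury from the required screening cleaning is not collected as an adverse event.

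The size cannot be computed. A reader might try a percentage of the 222, or count every in-office child over the 28-day screening window. The first uses the wrong base, and no stopping rate is given to apply to it. The second ignores that screening may fall on the procedure day (11.6) and that OR lead-ins are screened too.

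The conclusion rests on the visible definitions, and on the redacted text not adding a table for these children. It does not touch the efficacy analyses or the sample size. It is worth correcting because it follows from a stated rule, it bears on the device's safety rates, and the change is cheap.

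**What to change.** 1. In Protocol 10.6 and 13.2.3 and SAP 6.3, define the in-office safety set as children in whom any Earset Sizer, any Earset or the lidocaine solution entered the ear canal. Section 13.6 then follows, since it refers to the set.
2. In the adverse event tables, show children with device contact but no drug as a separate row, so that rates in drug-exposed children are not diluted.
3. In Protocol 12.1 and Table 4, record from consent any adverse event attributed to a study-required assessment, including screening ear cleaning, and add the screening tick.

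The cost is wording in those places and one item at screening. The safety denominator becomes slightly larger, and a few more minor events may be reported. Examinations done before consent would still not be covered.

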10.7. Secondary Effectiveness Endpoints

10.7.1. Tube Patency

Tube Patency: Tube Patency is the proportion of subjects in the pivotal cohort, in which a Tusker Medical tube was successfully placed, with functionally patent tubes in all successfully treated ears at the 3-week post-procedure follow-up visit.

The statistical test for the pivotal cohort Tube Patency endpoint is a hypothesis test against a Tube Patency performance goal.

10.7.2. Tube Retention

Tube Retention: Tube Retention is the proportion of subjects in the pivotal cohort, in which a Tusker Medical tube was successfully placed, with presence of a Tusker Medical tube across the tympanic membrane in all successfully treated ears at the 3-week post-procedure follow-up visit.

The statistical test for the pivotal cohort Tube Retention endpoint is a hypothesis test against a Tube Retention performance goal.

10.7.3. Anesthesia Effectiveness

Anesthesia Effectiveness: Proportion of subjects in the pivotal cohort, who completed iontophoresis for all indicated ears, with adequate anesthesia for TT placement in all treated ears as determined by physician's evaluation of TM anesthesia prior to TT placement.

The statistical test for the pivotal cohort Anesthesia Effectiveness endpoint is a hypothesis test against an Anesthesia Effectiveness performance goal.

The image consists of a series of horizontal black bars of varying lengths, arranged vertically. These bars represent redacted content, such as names or sensitive information, that has been obscured for privacy or security reasons. The lengths of the bars vary, indicating the length of the redacted text in each row.

This figure consists of a grid of black horizontal bars on a white background. The bars are organized into several groups, with some groups containing multiple bars and others containing a single bar. The lengths of the bars vary significantly, with some being very long and others very short. The bars are positioned in a staggered, non-overlapping manner across the grid.

This figure consists of a series of horizontal black bars of varying lengths, arranged in a grid-like pattern. The bars are positioned in rows, with some rows having more bars than others. The lengths of the bars vary significantly, with some being very short and others extending across the width of the image. There are also a few shorter bars positioned vertically on the left side of the image.

10.9. Inclusion Criteria

1. Males or females at least 6 months old through 12 years of age at time of consent.^{viii}
2. Indication for tympanostomy tube insertion per Clinical Practice Guideline (see **Section 11.4.1 Diagnosis**)¹

^{viii} Age 12 includes children who have not yet had their 13th birthday.

3. Behavioral capacity and cooperative temperament to undergo an awake procedure, based on physician judgment (*not applicable to OR Lead-In subjects*)
4. Subject's parent/guardian and subject are willing and able to comply with the protocol and attend all study visits.
5. Subject's parent/guardian and subject are willing and able to provide informed consent or assent as age appropriate.

10.10. Exclusion Criteria

1. Significantly atrophic, retracted, bimeric, monomeric or atelectatic tympanic membrane
2. Perforated tympanic membrane
3. Otitis externa
4. Active or recent conditions of the tympanic membrane (eg, prior myringotomy with incomplete wound healing or re-epithelialization)
5. Hemotympanum
6. Damaged/denuded skin in the auditory canal
7. Cerumen impaction resulting in a significant amount of cleaning required to visualize the tympanic membrane potentially causing abrasion or irritation to the external ear canal
8. Anatomy that precludes sufficient visualization of and access to the tympanic membrane
9. Anatomy that necessitates tympanostomy tube placement in the posterior half of the tympanic membrane
10. History of sensitivity or allergic reaction to lidocaine HCl, tetracaine, epinephrine, or any hypersensitivity to local anesthetics of the amide type, or any component* of the anesthetic drug formulation (*not applicable to OR Lead-In subjects*)

*Subjects with a known hypersensitivity to methylparaben and/or propylparaben (preservatives used in lidocaine HCl formulations), or to their metabolite para amino benzoic acid (PABA), or other components including potassium metabisulfite, sodium metabisulfite, edetate disodium or citric acid.

11. Familial history of insensitivity to lidocaine or other local anesthetics (eg, history of inadequate anesthesia with dental numbing agents). (*not applicable to OR Lead-In subjects*)

12. Electrically sensitive medical support systems (eg, pacemakers, defibrillators, cochlear implants) (*not applicable to OR Lead-In subjects*)
13. Other conditions that would preclude performing the study procedure including ear plug incompatibility
14. Health conditions that, in the opinion of the investigator, would present undue risk to the subject, based on device/anesthetic drug product label warnings and precautions
15. Subject is 4 years or older and not able to complete all baseline assessments. Subject is younger than 4 years and not able to complete all baseline assessments, not including audiometry.

Ear-specific exclusions (# 1-9, 13) apply to all indicated ears. Subjects may be indicated for unilateral or bilateral tube placement as described in **Section 11.4.1**. If a potential subject has both ears indicated for TT placement, but one ear does not meet the eligibility criteria, the subject is not eligible for the study because they would require an alternate treatment for the ineligible ear.

Investigators will document additional information to provide the rationale for exclusion for subjects not meeting inclusion criterion 3 (Behavioral capacity and cooperative temperament to undergo an awake procedure, based on physician judgment).

If a previously-determined eligible subject presents on the procedure day with a change in condition, such as an acutely infected ear or behavior non-compliance, the investigator may use clinical judgment to determine whether the condition as presented precludes performing the study procedure (Exclusion 13). The physician also has the option to re-schedule the procedure if the condition is transient.

11.0 STUDY PROCEDURES

11.1. Investigator Training

Investigators will be asked to refer to the drug package insert, device Instructions For Use (IFU) and the Investigator's Brochure for risks related to procedure, drug and device. The Investigators will be trained on use of the Iontophoresis and Tube Delivery Systems using a model system.

11.2. Lead-In Procedures

Each investigator will be required to enroll and conduct lead-in procedures prior to enrolling subjects to the pivotal cohort. Subjects enrolled to the lead-in cohorts must meet the same eligibility criteria and must complete the same protocol-required procedures and assessments as the pivotal cohort; however, their data will be separately analyzed and reported. Subjects undergoing OR procedures using general anesthesia must be suitable candidates for a surgical procedure under general anesthesia per Investigator's standard practice.

The lead-in procedure criteria are summarized below:

- 2 subjects ages 6 months through 12 years in the OR under general anesthesia using the TULA TDS (Stage 1), and

- 2 subjects ages 6 months through 12 years in-office using the TULA Iontophoresis and Tube Delivery Systems (conducted after Stage 2 approval).

Any investigator enrolling pediatric pivotal cohort in-office procedures must first complete OR lead-in procedures followed by lead-in in-office procedures for children. [REDACTED]

[REDACTED]

[REDACTED]

[REDACTED] Additional optional lead-in subjects may be enrolled at Investigator or Sponsor discretion in any of the categories listed above. Such selection must occur prior to enrollment of the subject into the study.

[REDACTED]

[REDACTED]

[REDACTED]

[REDACTED]

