10.2. Overall Study Design – Phases and Enrollment

This study is a prospective, single-arm, multicenter evaluation of safety and effectiveness of iontophoresis using the IPS and TDS for TT placement in-office for children indicated for tympanostomy tube placement.

[REDACTED] Study enrollment and procedures will occur in two stages.

Stage 1 (OR Lead-In Cohort): Stage 1 consists of tube placement procedures in the OR under general anesthesia. [REDACTED] each investigator will enroll 2 lead-in subjects in the operating room (OR) undergoing tube placement using the Tube Delivery System to place the tympanostomy tube(s) under general anesthesia (ie, no lidocaine iontophoresis). Stage 1 is comprised of the OR Lead-In Cohort (up to 100 subjects; further described in **Section 11.2**).

Stage 2 (In-Office Lead-In Cohort and Pivotal Cohort): Stage 2 consists of in-office procedures using both the lidocaine Iontophoresis System and the Tube Delivery System for the in-office tube placement procedure, including both the Office Lead-In Cohort and the Pivotal Cohort. [REDACTED]

[REDACTED] each investigator will enroll 2 lead-in subjects in-office undergoing tube placement using the TDS with local anesthesia facilitated by the Iontophoresis System (up to 100 subjects in the Lead-In Office Cohort). Investigators may enroll into the Pivotal Cohort following completion of their lead-in procedures. The pivotal cohort will include 222 children (ages 6 months through 12 years, inclusive) with evaluable data indicated for tympanostomy tube placement enrolled

at up to 25 investigational centers (minimum of 15 centers).ⁱⁱⁱ The pivotal phase will include 102 children ages 5 years and older, and 120 children less than 5 years of age with evaluable data.

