10.4.1. Definition of Enrollment

All subjects who consent for participation in the study are considered enrolled. Subjects who do not meet eligibility criteria are considered screen failures. **Section 13.0 Statistical Methods** provides further definition of subjects included in the analysis sets.

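### Could optional in-office lead-in subjects be used to steer difficult children out of the Procedural Success test?

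*Protocol*

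**What the plan says.** Protocol 11.2 requires each investigator to complete two OR lead-ins and then two in-office lead-ins, the latter given as "2 subjects ages 6 months through 12 years in-office using the TULA Iontophoresis and Tube Delivery Systems". It then adds: "Additional optional lead-in subjects may be enrolled at Investigator or Sponsor discretion in any of the categories listed above". The next sentence limits the timing: "Such selection must occur prior to enrollment of the subject into the study". Enrollment means consent (Protocol 10.4.1): "All subjects who consent for participation in the study are considered enrolled".

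Protocol 10.2 sets a study-wide ceiling of "up to 100 subjects in the Lead-In Office Cohort" and a sequence: "Investigators may enroll into the Pivotal Cohort following completion of their lead-in procedures". SAP 4.0 repeats the sequence and names the office lead-ins specifically.

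Lead-in and pivotal children meet the same eligibility criteria and have the same assessments (11.2). Lead-ins are excluded from the pivotal cohort (10.4.2.3) and analyzed and presented separately (10.4.2.2; SAP 5.2). Only the pivotal FAS is tested against 68% (13.3).

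In the public copy, redacted lines stand immediately before and after the two sentences on optional lead-ins, and Section 11.3 is redacted entirely.

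**The concern.** In a single-arm trial against a fixed goal, whoever decides which children enter the denominator can influence the result. Here an investigator or the sponsor may add lead-ins at discretion, and those children drop out of the primary test. The visible part of 11.2 names no maximum per investigator, asks for no reason and does not say in so many words when optional lead-ins stop.

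Fixing the label before consent does not remove all information. Otoscopy, for example, "may be obtained prior to study informed consent as a screening assessment within 28 days prior to procedure", and 11.4.5 and 11.4.6 say the same of tympanometry and audiometry. The investigator may also know the child. If children expected to do worse were made lead-ins, the pivotal rate would overstate success in the consecutive patients whom 11.5 says are offered the study, and the chance of wrongly passing the 68% goal would rise.

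**Working it through.** **1. Stated totals.** 102 + 120 = 222 pivotal children; 222 + 100 + 100 = 422. Both agree with Protocol 5.0. No power figure is visible to reproduce.

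**2. Room for optional lead-ins.** Optional in-office places = 100 − 2 × investigators. The plan states 15 to 25 centers but not the number of investigators, so that number is an assumption: 15 leave 70 places, 25 leave 50, 40 leave 20, and 50 leave none.

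**3. Reference rule.** The hierarchical model's details are not visible, so I use an exact binomial test without borrowing, at one-sided 0.025. For n = 102 and p = 0.68, P(X ≥ 79) = 0.0237 and P(X ≥ 78) = 0.0393, so 79 of 102 are needed.

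**4. Effect of outcome-related labelling.** Suppose true success is 68% across pivotal and diverted children together, and d children with success rate s are diverted. Spread over all pivotal ages, the pivotal rate becomes r = 0.68 + d(0.68 − s)/222. For d = 10 and s = 0.50: 0.68 + 10 × 0.18/222 = 0.6881. The false-pass chance for Test 1 is P(X ≥ 79) with X ~ Bin(102, r). Both d and s are assumptions.

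| Diverted | s = 0.60 | s = 0.50 | s = 0.40 |
|---|---|---|---|
| 5 | 2.6% | 2.9% | 3.2% |
| 10 | 2.8% | 3.5% | 4.3% |
| 20 | 3.4% | 5.1% | 7.4% |

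The pivotal rate rises by 0.2 points (5 × 0.08/222) to 2.5 points (20 × 0.28/222). If s = 0.68, nothing changes and the chance stays at 2.4%.

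Two harsher sets of assumptions:

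- All diverted children aged 5 to 12 (divide by 102 instead of 222): 5.4% for 10 at 50%, 11.0% for 20 at 50%, 21.6% for 20 at 40%.
- Fifty diverted over all ages, with success 10 to 20 points below 68%: 6.6% to 15.7%. This would use every optional place at 25 investigators.

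**5. What the plan leaves open to selection.**

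- *Outcome, earset fit, procedure-day behavior.* Earset sizing and the procedure follow consent, and the label precedes it. None of these can drive the label.
- *Poor cooperation at screening.* Protocol 11.4.4: "Patients who are uncooperative during ear exam and ear cleaning at screening are not eligible study candidates". This applies equally to in-office lead-in and pivotal children.
- *Temperament.* Inclusion criterion 3 (10.9) already lets the physician exclude a child unsuited to an awake procedure, and 10.10 requires the rationale to be documented. An investigator expecting failure has a documented way to leave the child out, so a lead-in label adds little selection.
- *Findings before consent.* Nothing in the documents says that otoscopy, tympanometry or audiometry predicts placement failure among children who meet the criteria.
- *Timing.* Protocol 11.2 requires lead-ins before pivotal enrollment, 10.2 permits pivotal enrollment once they are complete, and SAP 4.0 ties this to the office lead-ins. None exempts optional ones. On the natural reading, all of an investigator's in-office lead-ins are early cases, which is the purpose of a lead-in.
- *Visibility.* Subject numbers are consecutive (14.1), listings carry number and cohort (SAP 21.0), and lead-in results are shown separately. A reader can compare the cohorts.

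**The case for a change.** The best case for the concern is that the sequence rule follows the list of two plus two required procedures, and nothing visible expressly extends it to optional ones. The per-subject timing rule could also fit optional lead-ins chosen while pivotal enrollment is open. The plan asks for a documented rationale when a child fails the temperament criterion, but no matching record is visible for a lead-in label, which also removes the child from the primary test. Separate reporting can show a difference between cohorts, but it neither explains why a child was labelled nor corrects the pivotal rate. A clarification would cost only a few sentences.

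What stands is that one sentence would make the end point explicit, and that a large, strongly outcome-related diversion would matter. What does not stand is the step from there to a defect. The limits said to be missing belong where the public copy is blacked out, and text hidden by redaction is not text the plan lacks. A rule that optional lead-ins stop at the first pivotal subject would largely write down what the sequence rule already implies. A supportive analysis pooling optional lead-ins with the pivotal FAS would mix in the learning cases that the design deliberately separates, so a lower pooled rate could not tell steering from inexperience.

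**Conclusion.** The concern does not hold. Followed as written, the plan fixes cohort membership before consent and before any outcome, completes lead-ins ahead of pivotal enrollment, bounds their number and screens both in-office cohorts alike. The primary test then has its intended error rate unless investigators choose labels on expected outcome. That is a possibility in principle, and the documents contain no sign of it. In the mild scenarios the false-pass chance moves from 2.4% to between 2.6% and 2.8%. Larger values depend on assumed diversion numbers, success gaps and age mix.

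This rests on three assumptions: the sequence rule covers optional lead-ins, as its unqualified wording suggests; the binomial rule without borrowing is a fair stand-in for the model that is not visible; and the redacted text does not contradict what can be read.
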